4. STUDY POPULATION

4.1. Number of Subjects

A total of approximately 110 subjects with 110 nodules classified as TI-RADS 1-5 scheduled for biopsy will prospectively screened (subject signed inform consent) to get 100 evaluable nodules (acceptable OA images (via

ICL QA process) collected with acceptable cytology/histology final diagnosis data). It is expected that 10% of nodules will be enrollment failure leading to target evaluable analysis set of 100 nodules.

Enrollment failures in the study would consist of subjects who did not have acceptable OA images collected and/or valid cytopathology cell counts or histopathology considered adequate for diagnosis. (Cytopathology insufficiency rates vary from about 1.5% - 20%. Thyroid nodules that have undergone FNA, but have insufficient cellularity for cytopathologic assessment, cannot be used unless repeat FNA is performed and shows adequate cellularity for diagnosis).

4.2. Inclusion/Exclusion Criteria

Inclusion Criteria: Subjects must meet all of the following criteria to be included in the study:

1. Have been informed of the nature of the study and provided written informed consent, prior to initiation of any study activities;
2. Have an undiagnosed suspicious solid or mostly solid thyroid nodule.;
3. 18 years of age or older at the time of consent;
4. Are willing and able to complete all procedures and assessments in accordance with the clinical protocol; and,
5. Have received recommendation for and are scheduled for an ultrasound guided FNAB, ultrasound guided core biopsy, excisional biopsy, lobectomy or complete thyroidectomy of at least one thyroid nodule.

Exclusion Criteria: Subjects who meet any of the following criteria will be excluded from the study:

1. Are prisoners;
2. Have a condition or impediment (i.e., insect bites, poison ivy, open sores, chafing of the skin, scar, tattoos, moles, etc.); that could interfere with the intended field of view (within one probe length or 4 cm of the nodule),
3. Previous or on-going radioactive iodine treatment.
4. Nodule to be biopsied is greater than 3.0 cm in maximum diameter;
5. Is pregnant;
6. Have an acute or a chronic hematoma and/or acute ecchymosis of the thyroid;
7. Is experiencing photo-toxicity or photo-sensitivity or is undergoing treatment for a photo-sensitive condition such as porphyria or lupus erythematosus;
8. Patient has received chemotherapy for any type of cancer within 90 days from date of screening CDU;
9. Have had previous image guided FNAB or surgical biopsy of the target nodule of interest within the 45 days of baseline Imago Scan;
10. Patient has participated in a clinical study of an investigational drug or device within 3 months prior to screening CDU that may have an impact on clinical outcomes; and,
11. Patient has previously participated in this study.

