1.4. Imago Previous Studies

Early breast proof-of-concept studies provided the company with supporting data to modify and enhance diagnostic performance of the Imago real time opto-acoustic functional imaging characteristics performed at the wavelengths of Nd:YAG and Alexandrite lasers. Imago was also tested on gelatin phantoms simulating dense

breast with blood vessels having blood with various degrees of oxygen saturation. In-vitro experiments with various phantoms demonstrated that OA/US imaging is capable of not only visualizing shape and dimensions of blood vessels, but also differentiating deoxygenated blood from oxygenated blood.

PREVIOUSLY PERFORMED IN VIVO SENO BREAST STUDIES WITH IMAGIO

FEASIBILITY STUDY

A Feasibility Study was conducted using a total of 155 subjects to determine the ability of Imagio to help identify and define benign and malignant OA features. This study was conducted at CTRC and at South Texas Radiology Imaging Centers (STRIC). The Feasibility Study provided data to further develop the algorithm and to identify separate sets of features that characterize benign and malignant disease. The Feasibility Study included subjects with masses classified as either negative diagnostic ultrasound (NDU) results or positive diagnostic ultrasound (PDU) results. The masses had varying histopathologic diagnoses, sizes, locations, and depths. The Feasibility Study subjects also had varying ages, ethnicities, and races. These subject-specific characteristics are intended to identify any unusual subpopulations. To date, there are no such known exclusions other than subjects with obscured views and subjects on medications with the potential to activate photosensitive dermatologic conditions.

The Feasibility Study demonstrated 3 internal and 3 external OA features that correlate with benign vs. malignant mass histopathology [17-20]. The POM was significantly higher for malignant masses than for benign masses [21]. The specificity was 8% higher for Imagio than for CDU (24% for OA vs 16% for CDU) among those with benign disease, there was >40% relative reduction in the numbers with POM >2% in support of biopsy sparing [22]. There were no reported device related adverse events.

SYSTEM VERIFICATON STUDY

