A subsequent System Verification Study was performed, enrolling a total of 44 subjects. The study was conducted at STRIC to evaluate the dual-wavelength performance of the Imagio breast imaging system in detecting suspicious lesions and for final tuning of the algorithm prior to embarking upon the pilot phase of the PIONEER study. The objectives of the System Verification Study were met and further conclusions could be drawn. There were no reported adverse events.

PIONEER STUDY

The Pioneer Study was a prospective multi-center trial with 2105 subjects enrolled across 16 US clinical sites including CTRC. Subjects were prospectively enrolled upon confirmation of being BI-RADS 3, BI-RADS 4, or BI-RADS 5, as confirmed by CDU evaluation of the suspicious mass(es). Images were collected at the clinical sites and sent to an Independent Imaging Core Lab who processed and checked image quality prior to images being processed and read by 7 independent readers.

Of the 1,972 subjects in the Safety Population, the overall mean age 49.4 years; 44.7 years for benign subjects and 58.4 years for malignant (cancer) subjects, consistent with the age distribution at cancer diagnosis. Seventy-two subjects (<4%) were noted to have more than one Study mass.

The study had 1 primary effectiveness endpoint and 5 secondary effectiveness endpoints, all of which were achieved with statistical significance after accounting for multiplicity testing.

There were no serious adverse device effects (SADEs), UADEs or deaths reported during the Study. Ten subjects (0.5%) reported 11 AEs that were considered related to the OA procedure. None were serious, all were mild in severity.

MAESTRO STUDY

Five centers in the Netherlands participated in this prospective, controlled, multi-center, observational and post market surveillance study. Between March 2015 and February 2016, 217 patients with 223 mass lesions were included in this study. Three patients were excluded due to technical failure (not exposed to OA) and 5 were excluded due to the absence of a biopsy (patients' choice not to undergo further investigation). Therefore, 209 patients with 215 lesions were included in the intent-to-diagnose population. The mean age of these patients was 47.8 years (range 19 to 84). Sensitivity was 95.5% versus 100% for CDU. 53.3% of CDU BI-RADS 4b masses were upgraded.

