The primary objective of this study was to downgrade benign CDU BR 4a, 4b masses to OA BR 2-3 and to Not downgrade malignant CDU BR 4a, 4b masses to OA BR 2-3. Of the 146 benign lesions, 12.3% (18/146) were upgraded from BI-RADS 4a to 4b, 6.1% (9/146) were upgraded from BI-RADS 4b to 4c and 0.6% (1/146) was upgraded from 4b to 5. Among the 67 malignant lesions, 1.4% (1/67) was upgraded from BI-RADS 4a to 4b, 44.7% (30/67) were upgraded from BI-RADS 4b to 4c and 2.8% (2/67) were upgraded from 4b to 5. From the 215 lesions, 68.5% (146/215) were histologically as benign, 31.4% (67/215) were histologically malignant and 0.1% (2/215) were considered high-risk lesions histologically. Among the 146 histologically benign masses, 81.5% (119/146) were classified as BI-RADS 4a and 18.5% (27/146) were classified as BI-RADS 4b by CDU. Sixty benign lesions were correctly downgraded from BI-RADS 4a or 4b to 3 or 2 ($p < 0.0001$). From the benign lesions classified as BI-RADS 4a, 57 (48%) were downgraded to BI-RADS 3 or 2 according to OA ($p < 0.0001$), and from the 27 benign lesions classified as 4b, 6 (22%) were downgraded to BI-RADS 4a, 3 or 2 by OA ($p = 0.0471$). One adverse event was noted not related to OA which was a hematoma post biopsy.

PREVIOUSLY PERFORMED STUDIES WITH IMAGIO ON OTHER BODY STRUCTURES INCLUDING THE THYROID

PLATFORM STUDY

The Platform Study is an on-going early feasibility study designed to determine the ability of the Imagio OA device to image various body structures, thyroid being one of them. A total of 15 subjects have been enrolled in the study, 13 of which have undergone thyroid OA scans. The 13 subjects were comprised of 3 males and 10 females. The races of the enrolled subjects included 4 African American subjects and 9 Caucasian subjects. The study population included subjects ranging in ages of 22-60. There were 3 mild thyroid scan AEs reported consisting of tingling, pulsing, slight shock sensation.

The purpose of this project is to evaluate the performance of the Imagio device in distinguishing malignant from benign thyroid nodules using the Imagio ultrasound (IUS) and opto-acoustic (OA) component of the device and to refine the device algorithm specific to thyroid nodule diagnosis and to develop guidelines for interpretation of thyroid OA studies. The results will be used to further develop the pivotal study objectives and endpoints.

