6.3. Risk/Benefit Rationale

Seno Medical Instruments, Inc. believes that any potential risk presented by this investigation has been minimized and that adequate testing, safeguards, and safety monitoring have been incorporated into the investigation to further minimize and mitigate the risks.

The laser energy will be set to a level that is known as being below known harmful levels, which is unlikely to harm the thyroid or give any discomfort.

Also, everyone in the examination room will be wearing protective eyewear in order to minimize risk of damage by laser light to the eyes

Seno Medical Instruments, Inc. firmly believes that the value of the knowledge to be gained by conducting this clinical investigation to demonstrate the clinical value of the Imago™ Thyroid Imaging System outweighs the potential risks posed to participating subjects.

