7.2. Study Visits and Procedures

7.2.1. Screening/Enrollment/Imaging Visit- Day 1

The following procedures will be conducted at the Screening/Enrollment Visit:

- Perform informed consent;
- Review inclusion /exclusion criteria;
- verify from images and/or reports that a suspicious nodule was seen;
- Confirm that CDU has been performed, for which the site radiologist has recommended either ultrasound-guided FNA and/or US-guided core needle biopsy, and will fall within 365 days of Imago OA procedure.
- Record demographics and directed thyroid history; and,
- TI-RADS CDU-based classification
- Imago Imaging

Upon enrollment, subjects receive a subject number that will be used on all documentation for the subject throughout the study. Subject numbers should be assigned in ascending order, and numbers should not be omitted or reused. The subject number is coupled with the site identification number for unique identification of each subject.

Subjects will undergo the Imago OA procedure. Subjects may be asked to return to the clinic to repeat the Imago scan if (a) the image quality is not acceptable for review by A. [name]. Seno's Medical Director and/or the ICLs quality assurance reviewers (QARs) and (b) they have not yet undergone a biopsy procedure. Any adverse device effects or unanticipated adverse device effects that occur during this visit will be reported to appropriate authorities such as the IRB and FDA. In order to provide technical support, representatives from Seno Medical Instruments, Inc. or their designees may be present during the procedure.

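### Exclusion 7 does not cover a symptom-free subject taking a photosensitising drug for another indication, a group that section 1.4 lists among the known exclusions for the same device: a low-severity alignment

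*Combined protocol and SAP*

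**What the plan says.** Four parts of the protocol bear on this.

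- **Section 4.2, exclusion 7** removes a subject who "Is experiencing photo-toxicity or photo-sensitivity or is undergoing treatment for a photo-sensitive condition such as porphyria or lupus erythematosus".
- **Section 4.2, neighbouring criteria.** Exclusion 2 deals with skin conditions or impediments "that could interfere with the intended field of view". Exclusion 8 reads "Patient has received chemotherapy for any type of cancer within 90 days from date of screening CDU". Exclusion 10 covers recent participation in a study of an investigational drug or device that may affect clinical outcomes.
- **Section 1.4**, under the breast Feasibility Study, remarks that the only known exclusions so far are "subjects with obscured views and subjects on medications with the potential to activate photosensitive dermatologic conditions".
- **Day 1 procedures.** Section 7.2.1 includes the step "Review inclusion /exclusion criteria" and a directed thyroid history, and lists both ahead of the Imagio imaging. Table 1 also has a Medical History row. Neither place names a check of current medication.

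On safety, section 6.2 lists phototoxicity only in connection with fragrance or lotion on the skin. Section 6.3 gives the assurance "The laser energy will be set to a level that is known as being below known harmful levels". Section 6.1 says that participants do not benefit directly.

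**The concern.** Section 1.4 names two groups. The first, obscured views, has a counterpart in exclusion 2. The second, people on certain medications, has no full counterpart in 4.2. Exclusion 7 addresses photosensitivity, but through what the subject is experiencing now or what is being treated. It does not ask what the subject is taking.

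At stake is a small matter of subject protection and consistency. The protocol already treats photosensitivity as relevant to this laser, through exclusion 7 and the phototoxicity item in 6.2. It should not mention a medication group as a known exclusion and then admit that group without comment, least of all in a study without direct benefit to participants. The specificity endpoint is not at issue here.

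**Working it through.** **1. Is there a gap in the wording?** Take a subject with no current skin reaction who takes a photosensitising drug for an unrelated indication, and go through the criteria.

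| Provision | Does it remove this subject? |
|---|---|
| Exclusion 7, first limb (currently experiencing photo-toxicity or photo-sensitivity) | No: symptom-free |
| Exclusion 7, second limb (under treatment for a photo-sensitive condition) | No: the drug is for something else |
| Exclusion 8 (chemotherapy within 90 days of screening CDU) | Only if the drug is chemotherapy |
| Exclusion 10 (investigational product within 3 months) | Only if taken in such a study |
| Exclusion 2 (field of view) | No |
| 6.2, 6.3, Table 1, 7.2.1 | No eligibility rule and no medication check |

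The subject is eligible under 4.2, yet belongs to the medication group in 1.4. Section 5.1 confirms that the present study uses Imagio, so the device is the same.

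**2. What do the earlier data show?**

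- PIONEER: "Ten subjects (0.5%) reported 11 AEs that were considered related to the OA procedure. None were serious, all were mild in severity". With the Safety Population of 1,972 as denominator, 10 / 1,972 = 0.00507, or 0.51%, which agrees with the stated 0.5%. The exact (Clopper-Pearson) 95% interval is 0.24% to 0.93%. The protocol does not itemise the 11 events.
- MAESTRO: "One adverse event was noted not related to OA which was a hematoma post biopsy".
- Platform Study: 13 thyroid scans, with 3 mild events (tingling, pulsing, slight shock sensation).
- Breast Feasibility Study (155 subjects): no device-related events. System Verification Study (44 subjects): no adverse events.

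No phototoxic reaction is reported in any of these. None of the results is broken down by medication, and the documents do not say how many earlier subjects, if any, were taking such drugs. The PIONEER interval is for all subjects and cannot be carried over to this group.

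**3. What would the added exclusion cost in recruitment?** Section 4.1 plans about 110 consented subjects. The documents give no prevalence p of such medication, so p is assumed. To keep 110 after the new exclusion, the number to consent is 110 / (1 − p), rounded up.

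| Assumed p | 110 / (1 − p) | To consent | Extra |
|---|---|---|---|
| 1% | 111.1 | 112 | 2 |
| 5% | 115.8 | 116 | 6 |
| 10% | 122.2 | 123 | 13 |
| 20% | 137.5 | 138 | 28 |

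These figures measure the cost of the change. They say nothing about the size of the risk.

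**The case against.** The case for leaving 4.2 alone has four parts.

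- **Section 1.4 is background.** The remark follows a sentence about identifying unusual subpopulations in a breast study and is paired with an imaging limitation. It states no eligibility rule for this trial. This stands. A reader might infer that 4.2 breaks a safety rule which the protocol itself lays down. The documents do not support that, because they do not say whether the medication remark concerned safety or how it was applied.
- **Exclusion 7 may be the sponsor's considered answer.** It sets no limit on cause, so a drug reaction already present is covered, and a narrower criterion can be a legitimate choice. This stands in part. The wording describes a current state, so the symptom-free user is not caught on a plain reading, and no reason is given for the difference from 1.4.
- **No harm has been seen, and the laser energy is said to be below harmful levels.** This stands as far as it goes. A reader might infer that these subjects are known to be at risk. Nothing in the documents shows that. Equally, results not split by medication cannot rule it out.
- **The User Manual may already contraindicate such drugs.** This is possible. The manual is not among the documents, and section 3.2 requires scanning according to the device instructions. Even so, eligibility is decided from 4.2, and a contraindication found only in the manual would leave the two documents out of step.

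**Conclusion.** The gap in wording is real and its severity is low. Under 4.2 as written, a symptom-free subject taking a photosensitising drug for another indication may be scanned, apart from those caught by exclusions 8 and 10, although 1.4 lists such subjects among the known exclusions for the device to date. Closing the gap is a precaution and a matter of consistency; it does not respond to observed harm.

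The size of the risk in this group cannot be computed, because the documents give neither a phototoxicity rate nor the medication status of earlier subjects. The conclusion rests on a plain reading of exclusion 7 and on the documents available. The User Manual and the content of the Appendix D scanning protocol could not be checked.

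**What to change.** 1. Add a third limb to exclusion 7: current use of medication of the kind described in section 1.4, in that section's terms, as judged by the investigator.
2. Add a current-medication check to the Day 1 eligibility review in 7.2.1, before the Imagio scan. The Medical History row in Table 1 is a natural place to record it.
3. Ask the sponsor whether the User Manual already contraindicates such medication. If it does, use its wording or drug list in 4.2 so that sites decide alike.

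The cost is one clause and a brief check at an existing visit, with no new visit and no device change. The downsides are an unknown number of extra screen failures (2 to 28 more consented subjects over the assumed prevalences) and, without a drug list, some variation between sites in how the clause is applied.

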5. DESCRIPTION OF EXPERIMENTAL DESIGN AND METHODS

5.1. Study Device

The study will use Imago to generate OA/US images. Imago is an investigational device in the US.

Operator Credentials and Training

Experienced clinicians (or registered sonographers) will conduct all exams. Only radiologists or registered sonographers who have received approved training from Seno Medical Instruments, Inc. may perform the examinations. Clinician experience guidelines are included in the *Imagio User Manual*. The sponsor or a sponsor's representative may be present during the procedure to provide technical assistance, if required.

5.2. Cytopathology and/or Histopathology Review

All biopsied nodules will be analyzed by a designated Cytopathologist and/or Histopathologist. This may include the initial biopsy and/or any second core/surgical biopsy.

5.3. Comparators and Gold Standard

Imagio OA/US will be assessed as a diagnostic test in the classification of thyroid nodules.

The CDU will serve as the “control” for comparative purposes. The ACR-TI-RADS committee classification system will be used to assess the thyroid nodule and the decision to biopsy with no single diagnostic methodology used to make this decision. CDU represents the subject-specific diagnostic tests used to make the thyroid nodule classification and the decision to biopsy. *Imagio OA* may not be used to determine final thyroid nodule classification or the decision to biopsy. If available, any data for and/or carotid duplex sonography, CT, MRI, or PET/CT, PET will also be used for comparative purposes.

The histology obtained from FNAB, core biopsy, or surgical biopsy (at the nodule level) will serve as the gold standard.

5.4. Blinding

Subjects will not be blinded to best practice study procedures but will not have access to the *Imagio OA* evaluation result.

The site investigators will have access to all subject data including the *Imagio* images and videos, and will assess and document the results of the OA study by completing the electronic data entry form (eCRF).

The site investigators will have access to the background clinical information and to the subsequent histopathology report.

5.5. Treatment Compliance

The *Imagio* unit will be operated only by study personnel trained by Seno personnel or their representatives.

5.6. Packaging, Labeling, and Instructions for Use

Seno will ship *Imagio* devices to the participating site. Seno personnel will unpack and install the study device as well as conduct and document operator training for study personnel.

5.7. Storage and Accountability

Investigators will be responsible for ensuring that only authorized study personnel have access to the study device for study purposes in accordance with FDA guidelines.

6. RISKS AND BENEFITS OF THE INVESTIGATIONAL DEVICE AND CLINICAL INVESTIGATION

6.1. Anticipated Clinical Benefits

The Imago thyroid imaging system was designed to provide quick and precise evaluation of suspicious nodules (including both palpable and non-palpable nodules) or imaging findings when the thyroid nodule and when appropriate, suspicious cervical lymph node was first detected as an incidental finding on CDU, CT or MRI of the chest or neck, carotid duplex sonography, or on PET/CT.

If proven valuable, the Imago may contribute to a reduction in the number of biopsy procedures to be performed. Consequently, fewer patients will suffer from physical and emotional stress around the biopsy procedure and waiting period to get the result from the pathologist.

In this study, the results of the Imago scans do not determine whether or not biopsies need to be performed. The study participants will therefore not experience direct benefit. We hope that this study will contribute in the future to a more accurate diagnosis of thyroid nodules.

